9.2. Setting

For this study, data from patients treated at public or private healthcare facilities in Argentina, Brazil, Chile, Colombia, diagnosed with R/R B-cell ALL or AML between 01 January 2015 and 31 December 2019 will be considered for the analysis.

The eligibility period of 5 years was determined to increase the overall patient representativeness, and to allow ample follow-up to assess survival outcomes.

The study will be conducted in approximately 15 sites distributed across Argentina, Brazil, Chile, and Colombia, and is expected to enroll approximately 700 patients with R/R B-cell ALL and AML in a consecutive matter. To assure the representativeness of each country, the number of sites and the total expected enrolled patients will be limited according to the country, considering the prevalence/incidence of the diseases. These will be estimated after a country level feasibility assessment.

Data collection will occur in a period of up to 12 months following the independent ethics committee (IEC)/ institutional review board (IRB) approval and study set up. Patients will be consecutively enrolled, considering both target population, with no set proportion of AML and R/R B-cell ALL patients to be included in the study. However, it is expected a higher proportion of AML patients in the cohort. The study period will comprise since diagnosis date (index date) until the study enrollment or death, whichever comes earlier.

9.2.1. Inclusion Criteria

Patients must meet all of the following inclusion criteria to be eligible for inclusion in the study:

1. Patients with ≥ 18 years old at diagnosis;
2. Confirmed diagnosis of relapsed/refractory B-cell ALL or newly diagnosed of AML between 01 January 2015 and 31 December 2019, as documented in the medical chart and according to the physician's notes;
3. Patients that received at least one line of treatment for R/R B-cell ALL or denovo AML within the study period; for R/R B-cell ALL patients, data on previous therapy will also be collected if available.

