8.1. Primary Objective(s)

- To describe the clinical and demographics characteristics of newly diagnosed AML (and follow up treatment for R/R disease when available) and relapsed/refractory B-cell ALL patients.
- To assess treatment patterns in current practice of newly diagnosed AML and relapsed/refractory B-cell ALL patients.

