9.2.3. Study Definitions

- Patients with AML: patients with diagnosis of AML according to the physician's note in the medical chart participants.
- Patients with B-cell ALL R/R: B-cell ALL R/R is defined as ALL patients with type B - cell that are classified as relapsed and/or refractory according to medical chart.
- Concomitant medications: drug treatment for comorbidities, supportive and prophylaxis therapies, or to treat adverse events.
- Consolidation therapy: according to the medical chart. A shorter and more intense treatment phase to further reduce the number of cancer cells. Also called intensification therapy and postremission therapy.⁶⁶

- Death in aplasia: according to the medical chart. Deaths occurring ≥ 7 days following completion of initial treatment while cytopenic; with an aplastic or hypoplastic bone marrow obtained within 7 days of death, without evidence of persistent leukemia.¹⁰
- Death from indeterminate cause: according to the medical chart. Deaths occurring before completion of therapy, or <7 days following its completion; or deaths occurring ≥ 7 days following completion of initial therapy with no blasts in the blood, but no bone marrow examination available.¹⁰
- Genetic classification and response to therapy for patients with AML and relapsed/refractory treatments for patients with B cell ALL: according to the medical chart and exemplifications are described in [ANNEX 3. ADDITIONAL INFORMATION: Appendix 3](#) and [Appendix 4](#).¹⁰
- Induction therapy: according to the medical chart. The first treatment that is given to greatly reduce the extent of cancer.⁶⁶
- Intrathecal therapy: according to the medical chart. A treatment with cell-killing drugs that are injected into the brain and spinal fluid.⁶⁶
- Maintenance therapy: according to the medical chart. A treatment phase that is given to prolong good treatment results.⁶⁶
- Palliative therapy. according to the medical chart. Health care that includes symptom relief but not cancer treatment. Also sometimes called supportive care.⁶⁶
- Primary chemotherapy: one or more cell-killing drugs that are used to rid the body of cancer.⁶⁶
- Relapsed disease: according to the medical chart. The return or worsening of cancer after a period of improvement.
 - Hematologic relapse (after CRM RD, CR, CRi) Bone marrow blasts $\geq 5\%$; or reappearance of blasts in the blood; or development of extramedullary disease.

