9.3.1. Outcomes

9.3.1.1. Primary Outcomes

- Description of demographic and clinical presentation characteristics at the moment of relapsed/refractory B-cell ALL or AML diagnosis.
- Treatment description considering the front-line therapy and subsequent regimen(s) required for patients with relapsed/refractory B-cell ALL and AML, including any systemic chemotherapy, target therapy, hematopoietic stem cell transplantation (autologous/allogenic), intrathecal chemotherapy and palliative management.

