9.10. Other Aspects

All efforts are made in this protocol to reduce inclusion bias. Potential sources of bias in this study, and the approach(es) for addressing and minimizing these biases are discussed below.

Selection bias: may arise if the study sample differs substantively from the underlying target population of patients with B-cell ALL R/R or AML. To minimize selection bias, the study protocol has selected eligibility criteria that are as liberal as possible: age ≥ 18 , newly diagnosed B-cell ALL R/R or AML, and willing to consent, in case ICF waiver is not approved by the ethics committee. Patients will also be recruited from a heterogeneous reservoir of study sites. Finally, where applicable, minimal de-identified information, including the reason for nonparticipation, will be collected for patients who are not enrolled in the study to assess whether there may be any systematic differences between participants and non-participants.

Measurement bias: inaccurate assessment of study variables can occur in observational research. The present study will seek to limit measurement bias by instructing investigators to conduct their patient care in the customary fashion and that observations will be made in a nonintrusive manner that will focus on medical records and not infringe on Latin American healthcare provider's and patient interactions.

Bias due to Missing Data or Study Variables: reference is made to [Section 9.9](#) regarding strategies for handling missing data. Briefly, the impact of missing data on the analysis will be evaluated, and appropriate measures will be taken to address the missing information if any bias is likely.

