8.2.4. Study Population Definitions

Patients diagnosed with R/R B-cell ALL or newly AML that received at least one line of treatment for R/R B-cell ALL or newly AML within the study period.

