8.7.1. Analysis Sets

All final analyses identified in this SAP will be performed by IQVIA following Pfizer Authorization of this Statistical Analysis Plan and Database Lock process.

The all subjects enrolled (ENR) set will contain all patients screened for the study, including those who provided the informed consent and the ones enrolled with an informed consent waiver (deceased patients).

The full analysis set (FAS) will contain all eligible patients.

The safety analysis set (SAF) will contain all eligible patients who receive at least one documented dose of any Pfizer product.

If there is any doubt whether a subject was treated or not with a Pfizer product, they will be assumed treated for the purposes of analysis.

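### The analysis set holds treated patients only, but the objectives, design text and limitations do not say so, and OS counted from diagnosis adds guaranteed survival time

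*Protocol*

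**What the plan says.** **Entry.** Protocol 9.2.1 item 3 requires "Patients that received at least one line of treatment for R/R B-cell ALL or denovo AML within the study period". SAP 8.2.4 defines the population as patients "that received at least one line of treatment for R/R B-cell ALL or newly AML within the study period", and SAP 8.2.5.1 and 8.3.1 repeat the condition. SAP 8.7.1 adds: "The full analysis set (FAS) will contain all eligible patients".

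**Stated target.** The two primary objectives in Protocol 8.1 (repeated in SAP 7.1) begin "To describe the clinical and demographics characteristics of newly diagnosed AML" and "To assess treatment patterns in current practice of newly diagnosed AML and relapsed/refractory B-cell ALL patients". Neither says treated. Protocol 9.1 and SAP 8.1 state that every patient diagnosed in the 2015 to 2019 window will be included. The same sections do attach the word treated to the secondary results.

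**Bias and limitations.** Protocol 9.10 presents the criteria as about as permissive as they could be, and names age, diagnosis and consent but not the treatment line. It adds that, where applicable, "minimal de-identified information, including the reason for nonparticipation, will be collected for patients who are not enrolled in the study". Protocol 9.9 and SAP 8.8 discuss incomplete records and loss to follow-up, not untreated patients.

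**Palliative care.** The primary treatment outcome (Protocol 9.3.1.1) ends its list with "intrathecal chemotherapy and palliative management". Protocol 9.2.3 defines palliative therapy, as recorded in the chart, as "Health care that includes symptom relief but not cancer treatment". The same section makes whatever treatment or regimen is given first the first line, and 9.3.2 lists palliative care under treatment information.

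**Start of OS.** Protocol 9.3.1.2 uses treatment initiation. Protocol 9.7 allows diagnosis or treatment. SAP 8.3.2 uses diagnosis in item 8 and treatment initiation in item 9. SAP 8.7 and items 8 and 9 of SAP 8.7.2 allow either.

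**The concern.** The population that is analysed is narrower than the one the text describes. A reader of the front-line table would take its percentages as shares of newly diagnosed AML patients, when they are shares of those who started a line. Someone who died before treatment, or was managed without a line, is in neither numerator nor denominator. The study then cannot say how often newly diagnosed patients receive no treatment line, although describing current practice is a primary objective.

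Survival has a second problem. A patient must live long enough to start treatment in order to enter. If the clock starts at diagnosis, nobody can die in the interval before treatment, so the curve is flat there by design.

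**Working it through.** **1. The plan's own figure.** The only size figure is about 700 eligible patients. The country numbers in SAP 8.5 give 200 + 300 + 100 + 100 = 700, which agrees. The point does not depend on it. The documents give no untreated share, no regimen share and no interval from diagnosis to treatment.

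**2. Denominators.** Eligible means at least one line, and the full analysis set is all eligible patients. The no-treatment-line share in that set is therefore 0 whatever the true value.

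**3. Treatment shares.** Let u be the share of otherwise eligible diagnosed patients who never start a line (assumed, 10% to 40%). A share p among treated patients is p × (1 − u) of all diagnosed. With p = 60% (assumed):

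| u | Share of all diagnosed | Difference |
|---|---|---|
| 10% | 60 × 0.9 = 54% | 6 points |
| 20% | 60 × 0.8 = 48% | 12 points |
| 30% | 60 × 0.7 = 42% | 18 points |
| 40% | 60 × 0.6 = 36% | 24 points |

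For scale, the 95% half-width for a 50% proportion is 1.96 × √(0.25/700) = 3.7 points with all 700 patients in one group. With 300 patients it is 5.7 points.

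**4. Survival, if read as that of all diagnosed patients.** S(all) = (1 − u) × S(treated) + u × S(untreated), so the gap is u × [S(treated) − S(untreated)]. With assumed 1-year values of 50% and 5%, the gap is 0.45u: 4.5, 9.0, 13.5 and 18.0 points at u = 10%, 20%, 30% and 40%. With treated survival from 30% to 60% and untreated survival from 0% to 10%, it runs from 2.0 points (0.10 × 20) to 24.0 points (0.40 × 60). It is zero if u = 0 or if the two groups survive equally.

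**5. OS from diagnosis.** Let g be the time from diagnosis to first treatment. For every patient in the set, OS from diagnosis = g + OS from treatment, so survival up to g is 100% by the entry rule. If g were the same for all, the median from diagnosis would exceed the median from treatment by exactly g.

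**6. Does palliative care open a line?** Its definition in 9.2.3 excludes cancer treatment, which points to no. The line definition in 9.2.3, the primary outcome in 9.3.1.1 and the treatment variables in 9.3.2 leave room for yes. Protocol 7.3 also mentions palliative chemotherapy, which could be a line. The documents do not settle it, so sites may apply the entry rule differently.

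**The case against.** **The restriction is declared.** The abstract, the inclusion criteria and the SAP population definition all state it, and 9.1 calls the secondary results those of treated patients. A treatment-pattern study in treated patients is a sound design. This stands, and nothing here asks for wider eligibility. It does not explain why the objectives, the inclusion sentence in 9.1, the defence in 9.10 and both limitations sections leave the restriction out.

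**Palliative patients are not necessarily excluded.** A reader might infer that anyone managed palliatively from diagnosis can never enter, and that the front-line palliative row is empty by construction. The documents do not support that, because step 6 shows the question is open. Palliative care can also follow a first line. What is certain is narrower: patients with no line, under whichever reading is adopted, are absent.

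**Survival from treatment start is not biased by this.** Protocol 9.3.1.2 starts OS and EFS at treatment initiation, and RFS needs a remission. None of these is defined for a patient who was never treated, so adding such patients would change the quantity being estimated. This stands. Step 4 matters only if the figure is presented as survival of all diagnosed patients, and step 5 only where the clock starts at diagnosis.

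**Older patients and poorer access.** A reader might also infer that the effect is concentrated in patients aged 65 or more and in countries with less access. Protocol 7.3 says some elderly AML patients receive supportive care, which makes the age pattern plausible but gives no share. Protocol 7.4 concerns access to testing and targeted drugs across the region. It says nothing on receiving no treatment, or on differences among the four countries.

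**The count may not be clean.** The non-enrolment record is minimal and conditional, and nothing shows that it or the screened set holds the fields needed to check the exclusions. This stands and limits the fix.

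**Conclusion.** The point holds as a mismatch between the analysed and the described population, together with an inconsistent start of OS. Followed as written, treatment shares for treated patients would be reported under objectives about newly diagnosed patients, and OS from diagnosis would include time in which death was impossible by design.

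The direction for shares is arithmetic: for any u above zero, a share among treated patients exceeds the share among all diagnosed by the factor 1/(1 − u). The direction for survival also needs untreated patients to do worse, which is plausible but not quantified. No size can be established, since u, the 60% and all the survival values are assumptions. At an assumed u of 10%, the 6-point shift in shares and the 4.5-point survival gap are only modestly above the 3.7-point sampling half-width. The documents do not support a claim that survival is overstated in general.

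**What to change.** 1. Label the objectives, treatment-pattern tables and OS/EFS outputs *treated newly diagnosed AML* and *treated R/R B-cell ALL*. Reconcile Protocol 9.1 and 9.10 (and SAP 8.1) with criterion 3, and add the restriction to Protocol 9.9 and SAP 8.8.
2. Start OS at treatment initiation throughout, as Protocol 9.3.1.2 does, and align Protocol 9.7 and SAP 8.3.2, 8.7 and 8.7.2. If OS from diagnosis is kept as an extra, let patients join the risk set only from their first treatment date.
3. State whether palliative care or palliative chemotherapy recorded as initial management counts as a treatment line, and reconcile the definitions in 9.2.3 with 9.3.1.1 and 9.3.2. Do not force palliative care into a post-treatment category, since those sections may allow front-line entries.
4. Instruct sites to log patients who fail only criterion 3 in the non-enrolment record of 9.10 and the screened (ENR) set. As far as the log permits, print a no-treatment-line count by cohort, age band and country beside the front-line table, with shares of treated and of all diagnosed. Note that the exclusions may not be fully verified in these patients.

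**Cost.** Items 1 to 3 are wording and one programming choice. Item 4 adds a small screening-log burden, and more if sites must open charts to check exclusions. The percentages of all diagnosed will look less favourable.

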9.2.2. Exclusion Criteria

Patients meeting any of the following criteria will not be included in the study:

1. Patients with no medical chart available.
2. Patients with unreliable data as per investigator's opinion (eg, excessive missing data or inconsistency data).
3. Patients that have participated in any interventional clinical trial for relapsed/refractory B-cell ALL or AML at any moment. Patients under any compassionate use is allowed.
4. Patients with secondary AML.
5. Patients with any concomitant primary malignancy.
6. Patients with acute promyelocytic leukemia (APL).

9.2.3. Study Definitions

- Patients with AML: patients with diagnosis of AML according to the physician's note in the medical chart participants.
- Patients with B-cell ALL R/R: B-cell ALL R/R is defined as ALL patients with type B - cell that are classified as relapsed and/or refractory according to medical chart.
- Concomitant medications: drug treatment for comorbidities, supportive and prophylaxis therapies, or to treat adverse events.
- Consolidation therapy: according to the medical chart. A shorter and more intense treatment phase to further reduce the number of cancer cells. Also called intensification therapy and postremission therapy.⁶⁶

- Death in aplasia: according to the medical chart. Deaths occurring ≥ 7 days following completion of initial treatment while cytopenic; with an aplastic or hypoplastic bone marrow obtained within 7 days of death, without evidence of persistent leukemia.¹⁰
- Death from indeterminate cause: according to the medical chart. Deaths occurring before completion of therapy, or <7 days following its completion; or deaths occurring ≥ 7 days following completion of initial therapy with no blasts in the blood, but no bone marrow examination available.¹⁰
- Genetic classification and response to therapy for patients with AML and relapsed/refractory treatments for patients with B cell ALL: according to the medical chart and exemplifications are described in [ANNEX 3. ADDITIONAL INFORMATION: Appendix 3](#) and [Appendix 4](#).¹⁰
- Induction therapy: according to the medical chart. The first treatment that is given to greatly reduce the extent of cancer.⁶⁶
- Intrathecal therapy: according to the medical chart. A treatment with cell-killing drugs that are injected into the brain and spinal fluid.⁶⁶
- Maintenance therapy: according to the medical chart. A treatment phase that is given to prolong good treatment results.⁶⁶
- Palliative therapy. according to the medical chart. Health care that includes symptom relief but not cancer treatment. Also sometimes called supportive care.⁶⁶
- Primary chemotherapy: one or more cell-killing drugs that are used to rid the body of cancer.⁶⁶
- Relapsed disease: according to the medical chart. The return or worsening of cancer after a period of improvement.
 - Hematologic relapse (after CRM RD, CR, CRi) Bone marrow blasts $\geq 5\%$; or reappearance of blasts in the blood; or development of extramedullary disease.
 - Molecular relapse (after CRM RD) If studied pretreatment, reoccurrence of MRD as assessed by Real-time polymerase chain reaction (RT-qPCR) or by MFC.
- Re-admission: according to the medical chart, generally defined as a hospital admission, occurring ≤ 30 -days after the index admission.
- Re-induction therapy: according to the medical chart. After the first induction therapy fails.⁶⁷
- Refractory disease: a cancer that does not improve with treatment.⁶⁶
- Regimen: a plan for the dose, schedule, and length of treatment. A regimen can be a treatment that consists of one or combined (two or more) drugs.⁶⁶

- Remission: the absence of cancer signs and symptoms after treatment.⁶⁶
- Recurrence therapy: according to the medical chart. Treatment for cancer that has returned after a cancer-free period.⁶⁶
- Treatment failure: according to the medical chart. Refractory disease or Death in aplasia or Death from indeterminate cause.¹⁰
- Treatment lines: lines will be defined as distinct combinations. The initial treatment or regimen administered will be first line. Do not include a stem cell transplant, induction, consolidation or maintenance therapies in your counting of lines. A line of therapy ends and a new line of therapy begins when the patient discontinued treatment with a regimen; if a regimen was added to the ongoing treatment this should be considered a new line of therapy. If a drug within a combination is held or discontinued this should not be considered a new line of therapy.
- Treatment response
 - Complete remission or complete response (CR): a patient's response to treatment according to the medical chart. Usually, AML complete remission defined as no physical signs of leukemia, bone marrow with active hematopoiesis, <5% bone marrow blasts and more than $1 \times 10^9/l$ granulocytes and more than $100 \times 10^9/l$ platelets in the blood and no circulating leukemic blasts or evidence of extramedullary leukemia.¹⁰
 - Complete response with incomplete blood count recovery (CRi): also known as CR with incomplete hematologic recovery, also a patient's response to treatment according to the medical chart. Definition includes all CR criteria except for residual neutropenia ($<1.0 \times 10^9/L$ [$1000/\mu L$]) or thrombocytopenia ($<100 \times 10^9/L$ [$100\,000/\mu L$]).¹⁰
 - Partial remission: a patient's response to treatment according to the medical chart. All hematologic criteria of CR; decrease of bone marrow blast percentage to 5% to 25%; and decrease of pretreatment bone marrow blast percentage by at least 50%.¹⁰
 - Progressive disease (PD): according to the medical chart. Progressive disease is usually accompanied by a decline in ANC and platelets and increased transfusion requirement and decline in performance status or increase in symptoms. Evidence for an increase in bone marrow blast percentage and/or increase of absolute blast counts in the blood is defined by European LeukemiaNet (ELN).¹⁰ as:

- >50% increase in marrow blasts over baseline (a minimum 15% point increase is required in cases with <30% blasts at baseline; or persistent marrow blast percentage of >70% over at least 3 months; without at least a 100% improvement in absolute neutrophil count (ANC) to an absolute level ($>0.5 \times 10^9/\text{L}$ [500/ μL], and/or platelet count to $>50 \times 10^9/\text{L}$ [50 000/ μL] nontransfused). According to ELN recommendations, the date of progression should then be defined as of the first observation date; or
 - >50% increase in peripheral blasts (white blood cell (WBC) \times % blasts) to $>25 \times 10^9/\text{L}$ ($>25 000/\mu\text{L}$) (in the absence of differentiation syndrome); or
 - New extramedullary disease.
 - Refractory disease: according to the medical chart. No CR or CRi after 2 courses of intensive induction treatment; excluding patients with death in aplasia or death due to indeterminate cause.¹⁰
 - Relapse from CR or CRi: according to the medical chart.^{40,53}
 - Appearance of leukemic blasts in the peripheral blood.
 - Appearance of extramedullary disease.
 - $\geq 5\%$ blasts in the bone marrow not attributable to another cause (eg, recovery of normal cells following chemotherapy-induced aplasia).
 - If there are no circulating blasts and no extramedullary disease and the bone marrow blast percentage is $\geq 5\%$
 - Tumor Lysis Syndrome (TLS): according to the medical chart. Descriptive TLS criteria are described in [ANNEX 3. ADDITIONAL INFORMATION: Appendix 2⁶⁸](#)

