- Descriptive (median and CI(95%)) estimations of Kaplan-Meier) of time between treatment initiation and death in months;
- Time categorized count and percentages.

10. For all AML patients who achieved Complete remission/response (CR) or Complete remission/response with incomplete hematological/count recovery (CRI) at the end of treatment, the RFS analysis will consider the treatment end date until date of next treatment initiation or date of death, whichever comes first. This time-to-event analysis will be described using a Kaplan Meier plot, if appropriate.

newly AML

- Descriptive (median and CI(95%)) estimations of Kaplan-Meier) of RFS
- Time categorized count and percentages.

11. For newly AML patients, each treatment response (induction and consolidation therapy) will assess the proportion of patients who achieve complete remission (CR), complete remission with incomplete haematological recovery (CRI), complete remission without minimal residual disease (MDR-), partial remission (PR), and progressive disease. No statistical testing will be carried out. Only descriptive data will be reported (absolute number, frequency, mean \pm standard deviation, median, interquartile range, minimum or maximum) for.

Newly AML patients:

- Treatment response
 - CR,
 - CRI,
 - partial remission/response,
 - progressive disease,
 - refractory disease,
 - relapsed from CR or CRI or recurrent disease,
 - other
- Minimal residual disease (MRD) evaluation for patients that achieved CR or CRI and the diagnose method for MRD evaluation
- Patient status description

12. For R/R B-cell ALL patients, each treatment response (to rescue treatment) will access the proportion of patients with complete remission (CR), complete remission without minimal residual disease (MRD-), partial remission (PR), and progressive disease. No statistical testing will be carried out. Only descriptive data will be reported (absolute number, frequency, mean ± standard deviation, median, interquartile range, minimum or maximum) for.

R/R B-cell ALL patients:

- Treatment response
 - CR,
 - CRI,
 - partial remission/response,
 - progressive disease,
 - refractory disease,
 - relapsed from CR or CRI or recurrent disease,
 - other
- minimal residual disease (MRD) evaluation for patients that achieved CR or CRI and the diagnose method for MRD evaluation
- Patient status description

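### The salvage CR proportion in R/R B-cell ALL can include patients who already met the morphologic CR criteria when the rescue line began

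*Protocol*

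**What the plan says.** Protocol 9.2.3 describes relapse in two places.

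- *Relapsed disease* has a hematologic part (marrow blasts of at least 5%, or "reappearance of blasts in the blood; or development of extramedullary disease") and a molecular part: "Molecular relapse (after CRM RD) If studied pretreatment, reoccurrence of MRD as assessed by Real-time polymerase chain reaction (RT-qPCR) or by MFC".
- *Relapse from CR or CRi*, listed under treatment response, covers blood blasts, extramedullary disease, or at least 5% "blasts in the bone marrow not attributable to another cause". It has no molecular part.

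Entry rests on the chart. Protocol 9.2.1 asks for "Confirmed diagnosis of relapsed/refractory B-cell ALL or newly diagnosed of AML", and 9.2.3 describes the ALL cohort as "ALL patients with type B - cell that are classified as relapsed and/or refractory according to medical chart". Inclusion also needs at least one line of treatment for the R/R disease. Neither section sets a blast threshold, and no exclusion in 9.2.2 removes an MRD-only relapse.

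CR in 9.2.3, and morphologic CR in Annex 3 Appendix 4, are defined by marrow blasts below 5% and count recovery. Neither has an MRD condition.

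For the R/R B-cell ALL cohort, SAP 8.7.2 item 12 says that "each treatment response (to rescue treatment) will access the proportion of patients with complete remission (CR"), then lists the other categories. It does not ask what disease was present when the line began. MRD is evaluated only among patients already recorded as CR or CRi.

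**The concern.** A response proportion means something only if the patients in its denominator were not already in the response state at the start. Here the entry rule can admit patients whose only sign of relapse is MRD, and the response rule is morphologic. Such a patient satisfies the CR criteria before any rescue drug is given and, if nothing worsens, satisfies them afterwards whether or not the treatment did anything.

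At stake is the overall CR (and CR/CRi) proportion after rescue treatment in R/R B-cell ALL, which is a secondary outcome. It would be biased upward by an amount that depends on how often sites label MRD recurrence as relapse and treat it. A reader of the final report could not see how large that amount is. A larger sample would not reduce it.

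**Working it through.** The plan gives no target response rate, sample size calculation or precision statement for this outcome, so there is no figure to reproduce. The check is a reading of the definitions, followed by an illustration.

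**Step 1: follow one patient through the definitions.** Take a B-cell ALL patient in MRD-negative CR, with MRD studied before treatment, who then has "reoccurrence of MRD as assessed by Real-time polymerase chain reaction (RT-qPCR) or by MFC". Marrow blasts are below 5% and counts are normal.

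| Rule | Where | Result |
|---|---|---|
| Relapsed disease | Protocol 9.2.3 | Relapsed (molecular part) |
| Relapse from CR or CRi | Protocol 9.2.3 | Not relapsed |
| Cohort entry | Protocol 9.2.1, 9.2.3 | Enters if the chart says relapsed and a rescue line was given |
| CR criteria before rescue | Protocol 9.2.3; Appendix 4 | Already met |
| CR proportion after rescue | SAP 8.7.2 item 12 | In the denominator; in the numerator if recorded as CR |

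**Step 2: see whether another category would catch a non-response.** By the criteria in 9.2.3, partial remission needs a fall in marrow blasts to 5–25%, which is impossible from below 5%. Refractory disease means no CR or CRi. Progressive disease needs a marked blast increase or new extramedullary disease. So a patient whose MRD persists without worsening fits CR, or CRi if counts are low. The MRD-negative CR category is different: this patient starts MRD positive and must convert to be counted there.

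**Step 3: illustrate the size.** Let p be the CR rate among patients with overt disease at the start, m the share entering on MRD alone, and q the share of those recorded as CR at the end of the line.

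Apparent CR rate = p(1 − m) + qm

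- p = 0.40, the background figure for first salvage in Protocol 7.3.
- m is not in the documents; assumed.
- q is not in the documents; assumed 0.8 to 1.0.

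| m | q = 0.8 | q = 1.0 |
|---|---|---|
| 5% | 0.38 + 0.04 = 42% | 0.38 + 0.05 = 43% |
| 10% | 0.36 + 0.08 = 44% | 0.36 + 0.10 = 46% |
| 20% | 0.32 + 0.16 = 48% | 0.32 + 0.20 = 52% |
| 30% | 0.28 + 0.24 = 52% | 0.28 + 0.30 = 58% |

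At 5–10% the shift is 2 to 6 points. The 20% and 30% rows show only how the formula behaves; nothing in the documents points to shares that high.

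**Step 4: compare with sampling error.** The ALL cohort size is not given. For a 40% rate, the 95% half-width is 1.96 × √(0.40 × 0.60 / n). This is 9.6 points at an assumed n = 100 and 8.1 points at an assumed n = 140.

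**Step 5: apply the restriction.** With m = 0 in the denominator, the illustrative rate returns to 40%.

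**The case against.** The strongest reply is that neither glossary entry decides anything by itself. Entry is whatever is "classified as relapsed and/or refractory according to medical chart", response is also taken from the chart, and Protocol 9.3.2 tells abstractors not to interpret. An MRD-only patient enters only if a physician called the disease relapsed and gave a rescue line. The molecular part needs a prior MRD-negative CR and pretreatment MRD study. The CR text is worded as the usual AML definition, and a physician may not record a new CR for someone already in remission; item 12 also has an *other* category. All of this stands. It limits how often the problem arises and means that the size cannot be known. It does not remove the problem, because no rule in either document keeps such a patient out or sets the patient apart in the response table. For R/R B-cell ALL response, Protocol 9.2.3 points to Appendix 4, where morphologic CR is also free of any MRD condition.

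It is also fair to say that the two relapse entries serve different purposes, one as a general glossary term and the other as a response category. That makes them unreconciled rather than plainly contradictory.

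Three stronger readings are tempting and are not supported:

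- *That response rates would not be comparable between countries.* SAP 8.7.6 stratifies the primary objectives and EFS, OS and RFS by country, but not response.
- *That sites testing MRD would record AML relapse earlier and so distort survival outputs.* SAP 8.7 measures RFS from treatment end to next treatment or death. It dates an EFS event by treatment end (or next-line start) under a refractory or relapsed response code, or by death. Neither is dated by MRD recurrence, which could act on RFS only indirectly, through earlier treatment.
- *That the rate would rise to 52–58%.* That needs a molecular-only share of 20–30% with every such patient staying in CR. Protocol 7.4 describes limited access to molecular profiling in the region, which gives no support to shares of that order.

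**Conclusion.** The concern holds for one output: the overall CR (and CR/CRi) proportion after rescue treatment in R/R B-cell ALL. As written, the plan can count patients who were already in morphologic CR when the line began, and nothing in the tables would reveal it. The MRD-negative CR proportion is not inflated this way, and the primary objectives do not depend on it.

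The size cannot be determined from the documents. The 2–6 point illustration rests on three things: the 40% background rate, an assumed molecular-only share of 5–10%, and an assumed 80–100% of those patients recorded as CR. That shift is smaller than the sampling error at the assumed cohort sizes, but it runs in one direction and does not shrink with n. Since planned data should allow most patients to be separated, the change is worth making before the final analysis.

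**What to change.** In SAP 8.7.2 item 12, classify each R/R B-cell ALL patient at the start of the rescue line as:

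1. morphologic or extramedullary relapse, or refractory disease;
2. molecular-only relapse;
3. unknown.

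Use data already planned in SAP 8.7.2: laboratory exams before each line (item 2), and molecular and immunophenotyping results by line (item 3). Report CR/CRi in group 1 as the salvage response rate, show group 3 separately, and report conversion to MRD negative for group 2.

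In Protocol 9.2.3, reconcile the two relapse entries and state which one applies to which use. In the SAP, state whether response code 6, which combines relapse from CR or CRi with recurrent disease, includes MRD-only recurrence, because that code also feeds EFS.

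The cost is definition and SAP wording plus one derived variable. The denominator becomes somewhat smaller. Relapse type at index is not a listed variable in Protocol 9.3.2, and item 12 lists MRD only for patients who reached CR or CRi, so some patients will fall into the unknown group where pre-line marrow data are missing. Deriving the class from existing data avoids a new CRF field. That matters because SAP version 2.0 already followed a test on 20% of the entered data, and a new field could mean going back to the charts.
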